***Hypothesis 1:** Two weeks of at-home practice will result in better performance of respiratory control (maintenance of frequency and volume over time) in those who practice more, however, accurate performance of yogic breathing will be lesser in those with high thoracic injuries (T3-T6).*

***Objective 2:** To assess the respiratory and hemodynamic changes that accompany slow yogic breathing in spinal cord injury patients.*

***Hypothesis 2:** Respiratory rate will decrease, blood pressure will decrease, tidal volume will increase, and minute ventilation will remain unchanged during yogic slow breathing compared to spontaneous breathing.*

***Objective 3:** To discern the changes in the relationship between respiration, heart rate and blood pressure variabilities with yogic breathing.*

***Hypothesis 3:** Slow yogic breathing will shift the relationship between heart rate and blood pressure variabilities toward more synchronized heart rate and systemic blood pressure fluctuations.*

3. General Description of Study Design

This study will be a small (N= 20) prospective cohort study with a one-time unblinded intervention of 4 differing breathing techniques compared to paced breathing. Participants will receive a log for at-home practice and instruction lasting 45 minutes around D1 and D7 with the option to have on coaching session via MGB's Zoom application. On D14 the participant will be asked to sequentially execute the randomized breathing techniques. The lab visit will last approximately 1.5 hours, during which beat-by-beat

cardiovascular variables and breath-by-breath respiratory variables will be recorded while slow breathing. The total in-person time commitment is about 4 hours (**Figure 2**).

[figure not shown]

Figure 2: Study schema with a timeline of participant contact hours and days. There will be two moments of coached practice during a period of two weeks with at-home practice encouraged throughout the period. At the conclusion of the two weeks the breathing practices will be repeated in the laboratory while obtaining respiratory and cardiovascular measurements. *It is possible for the participants to schedule the second visit via MGB's Zoom application.

4. Subject Selection

a) Inclusion/Exclusion Criteria

We will complete studies on 20 individuals — men and women aged 18 to 60 years — with a spinal cord injury. A detailed medical history will be taken, and subjects will be selected based on the following:

Inclusion criteria:

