1. breath frequency (between 0.25 and 0.08 Hz)
2. Inspiratory – Expiratory ratio (I:E) or 'Duty Cycle'
3. with and without ujjayi (yogic throat constriction)
4. with and without inspiratory/expiratory breath holding

AT-HOME PRACTICE

At the end of the first visit the subject will be given a log to record their at-home practice of the breathing techniques they were coached on. Participants will also receive an information pamphlet and audio track with information about the exercises covered during the first coaching session.

b) Study Visits

Pre-Screening

All study subjects from the ExPD program at Spaulding Hospital will be preliminarily screened over the telephone to ensure that they meet preliminary eligibility requirements. Eligible members will be approached after their workouts by the co-investigator to ask permission to call for screening.

Screening

Subjects who meet preliminary eligibility criteria and are interested in participating will be called by the co-investigator to screen inclusion and exclusion criteria and to discuss additional information about the study. Participants will be sent the informed consent letter at least one week before the first visit. Informed consent will be obtained at Spaulding Rehabilitation Hospital, Cambridge.

Visit 1 — History, Baseline, 1st Coaching

During participants first visit the study procedures will be reviewed in detail with study staff, the subject will give a detailed health history and their written informed consent to the principal or co-investigator. The participant will then proceed to complete a baseline pulmonary function test (PFT) lasting about 30 minutes. Leaving about 45 minutes to cover relevant breathing techniques and exercises.

Visit 2 — 2nd Coaching

The second coaching visit can optionally be completed via MGB's Zoom application and will be shorter and more focused on questions, concerns, or struggles of the participant.

Visit 3 — Breathing & Measurement

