Two weeks after inclusion, the subjects will return to the cardiovascular laboratory for assessments. All subjects will be instructed to abstain from vigorous exercise for 1 day prior to each study to avoid autonomic and neuroendocrine effects of exercise. In addition, subjects will refrain from caffeine and alcohol for the previous 24 hours and be studied at least 2 hours after a meal. All breathing patterns and techniques will be practiced with the participant before the day of measurement and the participant will also be coached by a pre-recorded audio track during measurement.

Measurements

1) Pulmonary function test

All subjects will perform standard spirometry for spinal cord injury, as describe in (44). The same technician will test all subjects. Subjects will be seated with belts or pant waists loosened and with a nose clip. The maneuver will be demonstrated, and instructions will be given to inhale completely and "blast" the air out. The subject will be encouraged to exhale maximally and sustain the effort at least 6 sec or longer, if possible, depending on the ability and willingness of the subject to continue. The volume-time curve will be recorded on a kymograph, and the flow-volume loop will be electronically displayed for review. An acceptable effort will be a minimum exhalation time of 6 sec with a rapid start and a well-defined early peak in flow that is smooth and continuous. Three acceptable efforts will be obtained.

2) CV Lab Measurement

Throughout the protocol, subjects will lie 30° supine and will be instrumented with a 5-lead EKG, pulse oximeter, finapress with sphygmomanometer, doppler, chest and abdominal belts, a microphone and a face mask with a two-way respiratory valve; for measurements of QRS-complex, SpO₂,

beat-by-beat arterial pressure, brachial blood flow, respiratory excursions, ujjayi sound mixed expired CO₂, ventilation and end-tidal CO₂.

After instrumentation and calibration, the subject will undergo a period acclimation with a resting breathing pattern for ~7 minutes. We will then record the breathing techniques for ~7 minutes each. Other than the acclimation period with resting breathing frequency the order of the other 5 breathing patterns will be randomized. Upon completion subjects will be asked to turn-in their two-week breathing logs. Participants will proceed to perform an exit-PFT and will then be finished with their contribution to the study.

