Note: Subjects that completed Lab Visit 3 before 5/19/23 will be invited back to repeat Lab Visit 3 with the addition of dead space ventilation measurements that has been added to this protocol.

7. Risks and Discomforts

The proposed study will utilize non-invasive cardiovascular and respiratory monitoring techniques with minimal risks. The attachment and removal of ECG electrodes and inflation of the blood pressure cuff may cause mild discomfort. Slow breathing may cause hypercapnia and lightheadedness, which quickly resolves when normal breathing resumes.

8. Benefits

a. Benefits to Participating Individuals

There are no direct benefits other than increased knowledge of different traditional breathing practices and their mental and physical effects.

Financial Compensation

Participants in this study will be compensated financially up to \$100USD relative to their time. As completion of all study visits is necessary for analysis participants will be paid \$20 for each study visit they complete. Payments will be made via check and participants SSN will be collected.

Note: Subjects that have already completed the protocol and repeat the LabVisit 3 protocol will be paid \$20 for this additional visit.

b. Benefits to Society

This research may help physicians and scientists to better understand how slow breathing patterns influence the cardiovascular system in persons with SCI, potentially informing future interventional studies in this population.

9. Statistical Analysis

Specific data variables being collected: We will collect data on RR interval, heart rate, blood oxygenation, beat-to-beat blood pressure, brachial blood flow, breathing frequency/depth, ventilation volumes and end-tidal carbon dioxide levels.

b) Data analysis

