Data analysis will begin with summary of important variables. Continuous data will be summarized using means and standard deviations, and categorical data will be summarized using frequencies and proportions. Spectral analysis will be used when appropriate. Mean values for these variables will be compared within subjects using t-tests or Wilcoxon Rank Sum tests. Effects of the important covariates including age, BMI, time since injury, and level of injury will be adjusted for via regression analysis. Co-variables will be compared using a t-test or Wilcoxon Rank Sum test in case of continuous variables and they will be compared using chi-squared test and Fisher's Exact test. Significant co-variables will be used in the above regression analysis.

10. Monitoring and Quality Assurance

As these studies represent physiologic investigation and not clinical trials, no formal quality assurance programs will be implemented but will be overseen by the principal and co-investigators.

Safety

All volunteers will be thoroughly screened prior to study. Studies are conducted in a well-supervised hospital facility and subjects are under constant observation by skilled professionals. Appropriately trained laboratory personnel are present during the procedures and continuous cardiovascular monitoring is performed. Procedures are stopped if the volunteer exhibits potentially serious side effects. In the event of adverse reactions or emergency, resuscitation equipment and medical care are immediately available at Spaulding Rehabilitation Hospital. All volunteers are provided a contact number should there be any complications following study.

Adverse Events

Any adverse events will be promptly reported to the Human Research Committee for review according to HRC guidelines. Serious adverse events either expected or unexpected will be reported immediately (within 24 hours of event) by telephone, fax or email followed by a full written report using the PHRC Adverse Event Form within 10 working days/14 calendar days. Mild to moderate unexpected or expected adverse events will be reported in writing using the PHRC Adverse Event Form within 20 working days/30 calendar days.

Confidentiality

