APPENDIX A

Data Monitoring Committee / Data and Safety Monitoring Board Appendix

- *To be completed for studies monitored by Data Monitoring Committee (DMC) or Data and Safety Monitoring Board (DSMB) if a full DMC/DSMB charter is not available at the time of initial IRB review.*
- *DMC/DSMB Charter and/or Roster can be submitted to the IRB later via Amendment, though these are not required.*

A Data Monitoring Committee (DMC) or Data and Safety Monitoring Board (DSMB) will be convened for safety monitoring of this research study. The following characteristics describe the DMC/DSMB convened for this study (Check all that apply):

- ☐ The DMC/DSMB is independent from the study team and study sponsor.
- ☐ A process has been implemented to ensure absence of conflicts of interest by DMC/DSMB members.
- ☐ The DMC/DSMB has the authority to intervene on study progress in the event of safety concerns, e.g., to suspend or terminate a study if new safety concerns have been identified or need to be investigated.
- ☐ Describe number and types of (i.e., qualifications of) members:
Click or tap here to enter text.
- ☐ Describe planned frequency of meetings:
Click or tap here to enter text.
- ☐ DMC/DSMB reports with no findings (i.e., “continue without modifications”) will be submitted to the IRB at the time of Continuing Review.
- ☐ DMC/DSMB reports with findings/modifications required will be submitted promptly (within 5 business days/7 calendar days of becoming aware) to the IRB as an Other Event.

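### Symptoms during the two weeks of home breathing practice are not systematically asked about or recorded, so home adverse events are likely to be under-counted

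*Combined protocol and SAP*

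**What the plan says.** **Safeguards.** The Safety text in Section 10 says "Studies are conducted in a well-supervised hospital facility and subjects are under constant observation by skilled professionals" and "Appropriately trained laboratory personnel are present during the procedures and continuous cardiovascular monitoring is performed". It adds that procedures are stopped for potentially serious side effects and that resuscitation equipment is at hand in the hospital. Home practice is not mentioned there.

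**Home practice.** The Figure 2 legend in Section 3 says "There will be two moments of coached practice during a period of two weeks with at-home practice encouraged throughout the period". Objective 1 in Section 2 speaks of daily practice, and Hypothesis 1 rests on two weeks of it. No number of sessions or minutes is set.

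**Risk.** Section 7 says "Slow breathing may cause hypercapnia and lightheadedness" and describes these effects as resolving quickly.

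**Records and contacts.** Under At-Home Practice in Section 6, "the subject will be given a log to record their at-home practice of the breathing techniques they were coached on". Visit 2, around day 7, is a coaching contact given over largely to the participant's difficulties, and it may be held by video. Under CV Lab Measurement, after the breathing recordings, "Upon completion subjects will be asked to turn-in their two-week breathing logs". The list of variables in Section 9 has no symptom item.

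**Reporting.** Section 10 requires all adverse events to be reported. Serious ones go within 24 hours. Mild to moderate ones, whether expected or not, are reported in writing within 20 working days. It also says "All volunteers are provided a contact number should there be any complications following study".

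**The concern.** The exposure with a named risk occurs in two settings, and the protocol describes safeguards for only one. In the laboratory, a symptom is seen by staff and accompanied by recorded physiology. At home, it becomes known only if the participant chooses to mention it.

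Two things are at stake. First, the reporting duty in Section 10 covers mild and expected events, which are the kind a participant is least likely to volunteer. A final statement that no adverse events occurred could then be read as covering home practice when it would mainly reflect the supervised sessions. Second, the log reaches the team after the participant has already repeated the patterns at Visit 3, so anything written in it comes too late to be known before that session.

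**Working it through.** The plan states no figure on this point, so there is none to reproduce. The check has four steps.

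**1. Is a home symptom foreseeable from the protocol's own text?** Section 7 attributes lightheadedness and hypercapnia to slow breathing itself, not to the laboratory setting. Section 6 lists breath holding among the features that vary. Hypothesis 2 predicts a fall in blood pressure, while Section 1 describes persistent hypotension with injuries above T6 and Section 4 admits participants on blood-pressure support. So it is foreseeable.

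**2. How much breathing is unsupervised?**
- Coaching: 45 min around day 1 and day 7 (Section 3, read as 45 min each) = 2 × 45 = 90 min. All of it is counted as breathing, which overstates supervised time.
- Laboratory: 5 patterns × about 7 min (Section 6) = 35 min, for one attendance at Visit 3.
- Supervised total: 90 + 35 = 125 min. If Visit 2 is by video, the in-hospital total is 45 + 35 = 80 min.
- Break-even home practice over 14 days: 125/14 = 8.9 min/day, or 80/14 = 5.7 min/day. Over 13 days: 9.6 or 6.2 min/day.

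Home share = 14m / (14m + supervised minutes), where m is minutes per day. The values of m are assumptions:

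| m (min/day) | Home min | Share against 125 min | Share against 80 min |
|---|---|---|---|
| 5 | 70 | 36% | 47% |
| 10 | 140 | 53% | 64% |
| 20 | 280 | 69% | 78% |
| 30 | 420 | 77% | 84% |

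The share is substantial throughout. It passes one half only above roughly 6 to 9 min/day.

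**3. What happens to a home symptom?**
- *On day 3:* it may come up at Visit 2, if the participant raises it. No question is specified and no field is described in which to write the answer.
- *On day 10:* no scheduled contact is described before Visit 3. It is known beforehand only if the participant makes contact, and the log is read after the recordings.
- *In both cases:* the reporting clocks in Section 10 start only if the event becomes known.

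**4. Would a count of zero be informative?** Let p be the chance that a participant has at least one home symptom in two weeks (an assumption, with participants independent). With N = 20, the chance that at least one participant is affected is 1 − (1 − p)^20. This is 64% at p = 5%, 88% at 10% and 99% at 20%. Even at modest rates, some home event is more likely than not, so a zero obtained without asking says little.

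**The case against.** Much can be said for the plan.

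- **A reader might infer that the observation sentence is false.** The documents do not support that. Section 6 uses the word study for a laboratory session when giving the pre-visit restrictions, and the next sentences in Section 10 concern laboratory staff and procedures. It is a gap in scope, not a misstatement.
- **A reader might infer that home symptoms are simply missed.** That is too strong. Visit 2 is one-on-one and directed at the participant's problems, a contact number is provided, and the duty to report adverse events is not confined to the laboratory. The number is worded for complications after study. On the session-based reading it may already cover the time after Visit 1, but this is not stated.
- **A reader might infer that most exposure is unsupervised.** No document figure shows this. Practice is encouraged, not prescribed, and at 5 min/day it is the smaller part.
- **The log form, pamphlet and consent pages are not available here.** That the log records practice only rests on its description. If the form has a symptom field, that part of the point falls away.
- **The named effects are transient**, and Visit 3 is closely monitored, so repeating the patterns there is not unguarded.
- **Appendix A** says that a monitoring board "will be convened for safety monitoring of this research study", while Section 10 gives oversight to the investigators. But the appendix is a conditional template with every item blank, and most naturally reads as not applicable. It is housekeeping.

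These arguments limit the size of the point. None of them supplies a step that asks about home symptoms, or a reason to read the log after the recordings instead of before.

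**Conclusion.** The point holds as a gap in adverse-event collection that is cheap to close. Section 10's safeguards describe the laboratory sessions. Home symptoms can be volunteered but are not systematically sought or recorded, and the log arrives after the Visit 3 recordings. Under-counting of mild home events is therefore likely. Its extent cannot be computed, because the documents give neither symptom rates nor daily practice time.

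The conclusion rests on two assumptions: that the log matches its description, and that no unseen form asks about symptoms.

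A reader might go further and infer that the gap biases Hypothesis 1, because people with symptoms practise less and perform worse. The documents do not establish this. The amount of practice is self-selected and open to confounding whatever the log contains, and one symptom item in 20 people would not separate the explanations. Home symptoms can be shown beside the practice results as description, no more.

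**What to change.** 1. Add a short line to the existing home log: symptoms during or after practice (none / lightheaded / breathless / other), and practice cut short (yes / no).
2. State that the coach asks about these items at Visit 2, in person or by video, and notes the answer.
3. Move review of the log to the start of Visit 3, before the recordings. What then follows for a participant with symptoms is for the investigators, and no rule is proposed here.
4. Send positive answers through the adverse-event reporting already in Section 10, and state that the contact number applies during the home period.
5. Limit any statement that no adverse events occurred to the periods in which symptoms were actively asked about.
6. As housekeeping, mark Appendix A as not applicable if no board is convened.

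**Cost.** A few minutes at two contacts that already exist, one form revision, and more mild events to report. The note at the end of Section 6 allows for participants who completed Visit 3 before this protocol version. They will have no comparable home symptom data, so the report should give the number of participants who were actually asked.

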APPENDIX A

Data Monitoring Committee / Data and Safety Monitoring Board Appendix

- *To be completed for studies monitored by Data Monitoring Committee (DMC) or Data and Safety Monitoring Board (DSMB) if a full DMC/DSMB charter is not available at the time of initial IRB review.*
- *DMC/DSMB Charter and/or Roster can be submitted to the IRB later via Amendment, though these are not required.*

A Data Monitoring Committee (DMC) or Data and Safety Monitoring Board (DSMB) will be convened for safety monitoring of this research study. The following characteristics describe the DMC/DSMB convened for this study (Check all that apply):

- ☐ The DMC/DSMB is independent from the study team and study sponsor.
- ☐ A process has been implemented to ensure absence of conflicts of interest by DMC/DSMB members.
- ☐ The DMC/DSMB has the authority to intervene on study progress in the event of safety concerns, e.g., to suspend or terminate a study if new safety concerns have been identified or need to be investigated.
- ☐ Describe number and types of (i.e., qualifications of) members:
Click or tap here to enter text.
- ☐ Describe planned frequency of meetings:
Click or tap here to enter text.
- ☐ DMC/DSMB reports with no findings (i.e., “continue without modifications”) will be submitted to the IRB at the time of Continuing Review.
- ☐ DMC/DSMB reports with findings/modifications required will be submitted promptly (within 5 business days/7 calendar days of becoming aware) to the IRB as an Other Event.
